## **8.6 SKIN RASH**

In controlled clinical trials, 26% (266/1008) of patients treated with 600 mg efavirenz experienced new-onset skin rash compared with 17% (111/635) of patients treated in control groups. Rash associated with blistering, moist desquamation, or ulceration occurred in 0.9% (9/1008) of patients treated with efavirenz. The incidence of Grade 4 rash (e.g., erythema multiforme, Stevens-Johnson syndrome) in patients treated with efavirenz in all studies and expanded access was 0.1%. Rashes are usually mild-to-moderate maculopapular skin eruptions that occur within the first 2 weeks of initiating therapy with efavirenz (median time to onset of rash in adults was 11 days) and, in most patients continuing therapy with efavirenz, rash resolves within 1 month (median duration, 16 days). The discontinuation rate for rash in clinical trials was 1.7% (17/1008). Co-formulated emtricitabine/tenofovir DF/efavirenz can be reinitiated in patients interrupting therapy because of rash.

Co-formulated emtricitabine/tenofovir DF/efavirenz should be discontinued in patients developing severe rash associated with blistering, desquamation, mucosal involvement, or fever. Appropriate antihistamines and/or corticosteroids may improve the tolerability and hasten the resolution of rash.

Experience with efavirenz in patients who discontinued other antiretroviral agents of the NNRTI class is limited. Nineteen patients who discontinued nevirapine because of rash have been treated with efavirenz. Nine of these patients developed mild-to-moderate rash while receiving therapy with efavirenz, and two of these patients discontinued because of rash.

## **8.7 LIVER ENZYMES**

In patients with known or suspected history of hepatitis B or C infection and in patients treated with other medications associated with liver toxicity, monitoring of liver enzymes is

recommended. In patients with persistent elevations of serum transaminases to greater than five times the upper limit of the normal range, the benefit of continued therapy with co-formulated emtricitabine/tenofovir DF/efavirenz needs to be weighed against the unknown risks of significant liver toxicity.

Because of the extensive cytochrome P450 mediated metabolism of efavirenz and limited clinical experience in patients with hepatic impairment, caution should be exercised in administering co-formulated emtricitabine/tenofovir DF/efavirenz to these patients.

## **8.8 BONE EFFECTS OF TENOFOVIR DF**

### *Bone Mineral Density:*

In clinical trials in HIV-1 infected adults, tenofovir DF (a component of STRIBILD) was associated with slightly greater decreases in bone mineral density (BMD) and increases in biochemical markers of bone metabolism, suggesting increased bone turnover relative to comparators. Serum parathyroid hormone levels and 1.25 Vitamin D levels were also higher in subjects receiving tenofovir DF.

The effects of tenofovir DF-associated changes in BMD and biochemical markers on long-term bone health and future fracture risk are unknown. Assessment of BMD should be considered for HIV-1 infected patients who have a history of pathologic bone fracture or other risk factors for osteoporosis or bone loss. Although the effect of supplementation with calcium and vitamin D was not studied, such supplementation may be beneficial in all patients. If bone abnormalities are suspected, then appropriate consultation should be obtained.

### *Mineralization Defects:*

Cases of osteomalacia associated with proximal renal tubulopathy, manifested as bone pain or pain in extremities and which may contribute to fractures, have been reported in association with the use of tenofovir DF. Arthralgias and muscle pain or weakness have also been reported in cases of proximal renal tubulopathy. Hypophosphatemia and osteomalacia secondary to proximal renal tubulopathy should be considered in patients at risk of renal dysfunction who present with persistent or worsening bone or muscle symptoms while receiving products containing tenofovir DF.

## **8.9 CONVULSIONS**

Convulsions have been observed in patients receiving efavirenz, generally in the presence of known medical history of seizures. Caution must be taken in any patient with a history of seizures.

Patients who are receiving concomitant anticonvulsant medications primarily metabolized by the liver, such as phenytoin and phenobarbital, may require periodic monitoring of plasma levels.

## **8.10 FAT REDISTRIBUTION**

Redistribution/accumulation of body fat including central obesity, dorsocervical fat enlargement (buffalo hump), peripheral wasting, facial wasting, breast enlargement, and "cushingoid

appearance" have been observed in patients receiving antiretroviral therapy. The mechanism and long-term consequences of these events are currently unknown. A causal relationship has not been established.

### **8.11 IMMUNE RECONSTITUTION SYNDROME**

Immune reconstitution syndrome has been reported in patients treated with combination antiretroviral therapy,.. During the initial phase of combination antiretroviral treatment, patients whose immune system responds may develop an inflammatory response to indolent or residual opportunistic infections (such as *Mycobacterium avium* infection, cytomegalovirus, *Pneumocystis jiroveci* pneumonia (PCP), or tuberculosis), which may necessitate further evaluation and treatment.

Autoimmune disorders (such as Graves' disease, polymyositis, and Guillain-Barré syndrome) have also been reported to occur in the setting of immune reconstitution, however, the time to onset is more variable, and can occur many months after initiation of treatment.

### **8.12 CO-ADMINISTRATION WITH RELATED DRUGS**

Co-formulated elvitegravir/cobicistat/emtricitabine/tenofovir disoproxil fumarate is indicated for use as a complete regimen for the treatment of HIV-1 infection and co-administration with other antiretroviral products is not recommended.

Co-formulated elvitegravir/cobicistat/emtricitabine/tenofovir disoproxil fumarate is not recommended for coadministration with the following:

- emtricitabine or tenofovir DF (ATRIPLA, COMPLERA, EMTRIVA, TRUVADA, VIREAD)
- products containing lamivudine (COMBIVIR, EPIVIR, EPIVIR-HBV, EPZICOM, TRIZIVIR) or adefovir dipivoxil (HEPSERA)
- ritonavir (NORVIR, KALETRA)

Related drugs not for co-administration with co-formulated emtricitabine/tenofovir DF/efavirenz include EMTRIVA (emtricitabine), VIREAD (tenofovir DF), TRUVADA (emtricitabine/tenofovir DF), and SUSTIVA (efavirenz), which contain the same active components as the co-formulation offered in this trial. Due to similarities between emtricitabine and lamivudine, other drugs that should not co-administered include those containing lamivudine, like COMBIVIR®, EPIVIR™, EPIVIR-HBV™, EPZICOM™, or TRIZIVIR™.

## **9 TOXICITY MANAGEMENT**

Toxicity management guidelines take into consideration the fact that the subjects are started on their first antiretroviral drug regimen very early in the course of their HIV infection when long-term clinical benefits of antiretrovirals are unproven. Study treatment may be interrupted or discontinued at the discretion of the investigator and according to the severity of the adverse experience. However, investigators are reminded that the purpose of this study is to look at the effects of early treatment in general, not the effects of this particular regimen. Attempts should be made to continue antiretroviral treatment uninterrupted if possible. Thus, substitutions for

toxicity are allowed and would be preferable to the discontinuation or interruption of the entire regimen, if safety considerations permit. Alternate regimens will be provided for participants by the study for the duration of time that the participant remains in the study.

There will be no mandated drug interruptions or discontinuations for any Grade 1 or 2 toxicity, except for elevated creatinine. Subjects with symptomatic toxicity Grade  $\leq 2$  may continue to receive study treatment at the discretion of the investigator. Any allowed medication may be used to treat subjects for symptomatic toxicities, at the discretion of the investigator, except excluded medications as listed in section 5.3.3.

## **9.1 PROCEDURES FOR MODIFICATIONS FOR SPECIFIC SYMPTOMS**

### **9.1.1 Rash**

#### **9.1.1.1 Grade 1 or 2 Rash**

Study treatment should continue without interruption and the rash may be treated symptomatically with permitted antipyretic or antihistamine medications, but should be monitored closely by the local investigator.

#### **9.1.1.2 Grade 3 Rash**

All study treatment should be interrupted until the toxicity grade returns to Grade  $\leq 1$ , after which time study medications can be resumed or alternative antiretroviral medications may be initiated at the investigator's discretion upon consultation with the Protocol Chair. If Grade  $\geq 3$  rash persists for more than 4 weeks, or if Grade 3 rash recurs, then the offending agent should be permanently discontinued.

#### **9.1.1.3 Grade 4 Rash**

All study treatment should be interrupted for any Grade 4 rash or evidence of a Stevens-Johnson syndrome. Any resumption of study treatment or alternative antiretroviral medications should only be done upon consultation with the Protocol Chair.

### **9.1.2 Nausea and Vomiting**

#### **9.1.2.1 Grade 1 or 2**

Study treatment should continue without interruption. Subjects with Grade 1 and 2 nausea or vomiting may be treated symptomatically with permitted oral antiemetic therapies or antiemetic suppositories provided there is no suspicion of lactic acidosis or pancreatitis.

#### **9.1.2.2 Grade $\geq 3$**

Subjects with Grade  $\geq 3$  nausea and vomiting should interrupt all study treatment until the toxicity grade returns to Grade 2 or to baseline. However, substitutions to the treatment regimen, as opposed to interruption of the entire regimen, may be made at the investigator's discretion upon consultation with the Study Chair. If the nausea does not improve with the substitution, then all study treatment should be interrupted. Once the toxicity returns to Grade 2 or baseline, study medications may be resumed. If Grade  $\geq 3$  nausea and vomiting recurs upon

the resumption of study treatment, treatment should again be interrupted and alternative ART should be considered and discussed with the Study Chair. If Grade  $\geq 3$  nausea or vomiting persists for more than 4 weeks, then study treatment should be permanently discontinued.

### **9.1.3 Diarrhea**

#### **9.1.3.1 Grade 1 or 2**

All subjects with study drug-related diarrhea should initially be treated symptomatically with antidiarrheal medications such as loperamide, diphenoxylate, and/or an aluminum hydroxide antacid. Study drug administration may continue at the discretion of the investigator.

#### **9.1.3.2 Grade $\geq 3$ Diarrhea**

Grade  $\geq 3$  diarrhea that is unresponsive to antimotility agents should prompt interruption of all study treatment until resolution of diarrhea to Grade  $\leq 2$  or baseline. However, substitutions to the treatment regimen, as opposed to interruption of the entire regimen, may be made at the investigator's discretion upon consultation with the Study Chair. If the diarrhea does not improve with the substitution, then all study treatment should be interrupted. Once the toxicity returns to Grade 2 or baseline, study medications may be resumed. If Grade  $\geq 3$  diarrhea recurs upon the resumption of study treatment, all study treatment should be interrupted and alternative ART should be considered and discussed with the Protocol Chair. If Grade  $\geq 3$  diarrhea persists for more than 4 weeks, then study treatment should be permanently discontinued.

### **9.1.4 Symptomatic Hyperlactatemia**

Occurrence of lactic acidosis is expected to be very rare with the medication regimen used in this protocol. However, if an investigator suspects – due to symptoms or lab abnormality – lactic acidosis or symptomatic hyperlactatemia, a lactate level should be drawn.

Symptomatic hyperlactatemia will be defined as new, otherwise unexplained and persistent occurrence for  $>2$  weeks of one or more of the following in addition to an elevated lactate level:

- nausea and vomiting
- abdominal pain or gastric discomfort
- abdominal distention
- increased LFTs
- unexplained fatigue
- dyspnea
- motor weakness

If the lactate value is  $> 2 \times$  ULN, obtain a confirmatory lactate value as soon as possible, preferably within 1 week. Study treatment should be discontinued immediately if the confirmatory value remains  $> 2 \times$  ULN or if the site is unable to obtain a confirmatory value within 1 week. Determine lactate levels every 4 weeks until the lactate value returns to normal, at which time a new antiretroviral regimen may be constructed in consultation with the protocol team.

Management of symptomatic lactate value  $< 2 \times$  ULN will proceed at the discretion of the local

investigator. However, any modification of a subject's antiretroviral regimen should be made in consultation with the protocol team.

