**8 WARNINGS AND PRECAUTIONS**

**8.1 LACTIC ACIDOSIS/SEVERE HEPATOMEGALY WITH STEATOSIS**

Lactic acidosis and severe hepatomegaly with steatosis, including fatal cases, have been reported with the use of nucleoside analogs alone or in combination with other antiretrovirals. A majority of these cases have been in women. Obesity and prolonged nucleoside exposure may be risk factors. Particular caution should be exercised when administering nucleoside analogs to any patient with known risk factors for liver disease; however, cases have also been reported in patients with no known risk factors.

Treatment with co-formulated elvitegravir/cobicistat/emtricitabine/tenofovir disoproxil fumarate or co-formulated emtricitabine/tenofovir DF/efavirenz should be suspended in any patient who develops clinical or laboratory findings suggestive of lactic acidosis or pronounced hepatotoxicity (which may include hepatomegaly and steatosis even in the absence of marked transaminase elevations).

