Although cobicistat (a component of STRIBILD) may cause modest increases in serum creatinine and modest declines in estimated creatinine clearance without affecting renal glomerular function, patients who experience a confirmed increase in serum creatinine of greater than 0.4 mg per dL from baseline should be closely monitored for renal safety. The emtricitabine and tenofovir DF are primarily excreted by the kidney. Co-formulated elvitegravir/cobicistat/emtricitabine/tenofovir disoproxil fumarate and co-formulated emtricitabine/tenofovir DF/efavirenz should be discontinued if estimated creatinine clearance declines below 50 mL per minute as dose interval adjustment required for emtricitabine and tenofovir DF cannot be achieved with the fixed-dose combination tablet.

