#### **9.2.5 Renal Insufficiency**

Tenofovir DF substitution should occur for a confirmed creatinine clearance  $< 50$  ml/min until an underlying etiology is determined. If no other etiology is determined or the renal insufficiency improves with holding tenofovir DF, tenofovir DF should be permanently discontinued.

Baseline serum creatinine will be the mean of the screening and entry values. If at any time serum creatinine is increased  $>1.5$ -fold above baseline, the serum creatinine should be repeated as soon as possible (preferably within one week). Participants with confirmed serum creatinine increases  $>1.5$ -fold above baseline should undergo an evaluation for potential causes of decreased renal function. Participants with confirmed increase in serum creatinine  $>1.5$ -fold above baseline should have serum creatinine monitored more frequently, at the discretion of the site investigator, until serum creatinine either stabilizes or decreases to  $\leq 1.5$ -fold above baseline. Drug dosing adjustments should be done based on the calculated creatinine clearance.

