## **12.5 DISCONTINUATION OF STUDY AGENT DUE TO AN ADVERSE EVENT**

The Study Medical Director or his designee has authority to stop study agent for any participant due to clinical or laboratory AEs, and must stop study agent according to criteria defined in the safety monitoring section.

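### Sections 8 and 9 give conflicting stopping and restart instructions for lactic acidosis, severe rash and creatinine clearance below 50 mL/min, and the protocol does not say which section prevails

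*Combined protocol and SAP*

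**What the plan says.** **Lactic acidosis.** Section 8.1 states that treatment with either co-formulated tablet "should be suspended in any patient who develops clinical or laboratory findings suggestive of lactic acidosis or pronounced hepatotoxicity". It sets no lactate threshold and asks for no repeat test. Section 9.1.4 starts from the investigator's suspicion, raised by symptoms or a laboratory abnormality, and asks for a lactate level. A value above 2 x ULN is to be repeated promptly, ideally inside 1 week. Then: "Study treatment should be discontinued immediately if the confirmatory value remains" above 2 x ULN, or if the site cannot get a repeat in that week. Symptomatic values under 2 x ULN are left to the local investigator.

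**Rash.** Section 8.6 allows the efavirenz co-formulation (Atripla) to be restarted after an interruption for rash. It says separately that the same product "should be discontinued in patients developing severe rash associated with blistering, desquamation, mucosal involvement, or fever". Section 9.1.1.2 interrupts all study treatment for Grade 3 rash. Once the rash is Grade 1 or less, it permits the study drugs or alternatives, at the investigator's discretion and after consulting the Protocol Chair. The offending agent is stopped for good only if rash of Grade 3 or higher lasts over 4 weeks or Grade 3 rash comes back. Section 9.1.1.3 interrupts treatment for Grade 4 rash or Stevens-Johnson syndrome and adds: "Any resumption of study treatment or alternative antiretroviral medications should only be done upon consultation with the Protocol Chair".

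**Renal.** Section 8.5 discontinues both tablets when estimated clearance falls below 50 mL/min, because the "dose interval adjustment required for emtricitabine and tenofovir DF cannot be achieved with the fixed-dose combination tablet". Section 9.2.5 substitutes tenofovir DF at a confirmed value below 50 until a cause is found, and makes its removal permanent in stated cases. Its second paragraph, on creatinine rises of more than 1.5-fold, ends: "Drug dosing adjustments should be done based on the calculated creatinine clearance". Section 9.2.6 also replaces tenofovir DF alone, for low phosphate. Section 8.12 says Stribild "is indicated for use as a complete regimen for the treatment of HIV-1 infection and co-administration with other antiretroviral products is not recommended".

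**Which section governs.** Section 10.1 (drug-related toxicity) and Section 12.8 (laboratory adverse events) refer to Section 9. Under 12.5 the Study Medical Director or designee "must stop study agent according to criteria defined in the safety monitoring section". No section carries that title.

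**The concern.** The Section 8 statements cited here are worded as instructions, so they cannot be set aside as background to Section 9. A site that follows one section can depart from the other, and two sites can manage the same patient differently while each cites the protocol. Nobody reviewing the case could say whether a deviation had occurred. The physician with a mandatory stopping duty under 12.5 is sent to criteria that cannot be located. These are named serious risks of the study drugs; 8.1 itself notes fatal cases.

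**Working it through.** No sample-size or power figure is involved, so the check takes one patient per event through both sections and then sizes the problem.

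1. **Suspected lactic acidosis.**
   - Under 8.1, suggestive findings are enough to suspend treatment.
   - Under 9.1.4, the same suspicion leads to a blood draw. If the first value exceeds 2 x ULN, the earliest mandated stop is the repeat result and the latest is the 1-week limit. No hold is stated for the interval.
   - The difference in mandated stopping is therefore 0 to about 1 week, counted from the first raised value.
   - If the value is under 2 x ULN with symptoms, the difference is not one of time: 8.1 may already have suspended treatment, while 9.1.4 mandates nothing and leaves it to discretion.

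2. **Severe rash on Atripla with the features named in 8.6.**
   - Both sections stop the drug at onset.
   - Section 8.6 separates rash after which Atripla may be restarted from severe rash for which it should be discontinued.
   - Sections 9.1.1.2 and 9.1.1.3 grade by severity only and drop that distinction. Resumption of the same regimen stays open after Grade 3 rash and, on consultation, after Grade 4 rash or Stevens-Johnson syndrome.
   - The conflict is about re-challenge, not the initial stop.

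3. **Clearance below 50 mL/min.**
   - Both tablets contain tenofovir DF, so replacing it under 9.2.5 also takes the patient off the tablet, as 8.5 requires.
   - The first difference is confirmation: 9.2.5 requires it and 8.5 does not mention it.
   - The second is duration: 8.5 is unqualified, while 9.2.5 runs until a cause is found.
   - The third is fit: 9.2.5 and 9.2.6 speak of exchanging one component. The products listed in 6.3.3 are Stribild, Atripla, Truvada and efavirenz, with no separate elvitegravir or cobicistat. The general dosing sentence in 9.2.5 makes no exception for tablets that 8.5 says cannot be adjusted.

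4. **Expected numbers.**
   - Section 8.6 reports rash with blistering, moist desquamation or ulceration in 9/1008 = 0.89% of efavirenz-treated patients.
   - Assume half of Step 3 receives Atripla, since 4.1 says roughly half were already enrolled and would receive it.
   - With 200–250 enrolled (4.1): 100–125 on Atripla, and 0.0089 x 100 to 0.0089 x 125 = 0.9 to 1.1 cases.
   - With 150–180 enrolled (11.3, 75–90 in each of two groups): 75–90 on Atripla, and 0.7 to 0.8 cases.
   - Section 9.1.4 expects lactic acidosis to be very rare. The protocol gives no rate for clearance below 50; entry requires more than 70 mL/min (5.3.2).

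**The case against.** The best defence is that the two sections can mostly be read together. In 9.1.4 nothing orders treatment to continue while the repeat is awaited, and the opening of Section 9 lets the investigator interrupt at discretion, so suspending under 8.1 and then discontinuing under 9.1.4 could be a sequence. Section 8.6 itself permits restart after rash, its stop rule names Atripla only, and Section 9 requires consultation before resumption. How the 8.6 features map to Grade 3 or 4 depends on an external grading table. For renal events both sections remove tenofovir DF. Sections 10.1 and 12.8 point to Section 9.

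Much of this stands, and it rules out several stronger readings that a reader might infer:

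- *That the instructions are opposite.* They are not. For rash and renal events both sections stop drug first, and for lactic acidosis both can end in stopping.
- *That lactate stopping could lag by about 3 weeks.* The definition requiring symptoms for more than 2 weeks controls neither the draw nor the stop.
- *That 9.2.5 orders dose adjustment at the 50 mL/min threshold.* That sentence closes a different paragraph and names no threshold.
- *That a Stribild patient has no workable option.* Section 6.3.7.3 and the opening of Section 9 provide for study-supplied alternative regimens, and 8.12 concerns adding drugs to Stribild, not replacing it. Only the single-component wording does not fit.

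The defence does not remove the differences in trigger, re-challenge, confirmation and duration. The allowance in 9.2 for skipping confirmation when delay is poor practice is written for Grade 3 and 4 laboratory abnormalities under 9.2, not for 9.1.4. The pointers to Section 9 are not a precedence rule over Section 8, and 12.5 still cites a section that cannot be found.

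**Conclusion.** The point holds as an internal inconsistency in safety instructions. It is clearest for lactic acidosis, where mandated stopping can differ by up to about 1 week after a first raised lactate. That figure rests on reading the absence of a hold in 9.1.4 as no instruction to stop. For severe rash the conflict is whether Atripla may be resumed. For clearance below 50 mL/min it is confirmation, duration and component-level wording.

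Few events are expected: about 1 severe rash, assuming half of participants take Atripla and the 8.6 rate applies. That rate does not count mucosal involvement or fever alone. With a median rash onset of 11 days (8.6) and roughly half of participants already enrolled, some of that risk may have passed, though not for anyone still to start Atripla.

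A reader might infer that differing interruptions would distort the viral-load outcome. With so few events, the documents show no such effect. The case for correction is patient safety and consistent conduct across sites. Which clinical rule is right is not judged here.

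**What to change.** Reconcile three pairs of passages: 8.1 with 9.1.4, 8.6 with 9.1.1.2 and 9.1.1.3, and 8.5 with 9.2.5 and 9.2.6. For each event and each regimen, state one trigger, whether a value must be confirmed and what happens meanwhile, and whether the same regimen may be restarted and on whose decision. Word 9.2.5 and 9.2.6 so that the action can be carried out with the fixed-dose products, with a reference to 6.3.7.3 where a whole regimen is replaced, and say what the dosing sentence in 9.2.5 applies to. Replace the reference in 12.5 with the section that governs, and keep 10.1 and 12.8 consistent with it. The sponsor's clinicians must choose which rule stands in each pair.

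The cost is an amendment to the text of Sections 8, 9 and 12.5 with the usual ethics review. It adds no patients, visits or procedures.
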